5.4 Exclusion Criteria

Potential participants who meet the following criteria will be excluded from the study along with their partner:

1. Has any significant medical condition or other condition that, in the opinion of the Investigator of Record (IoR)/designee, would preclude informed consent, make study participation unsafe (including risk for IPV as a result of study participation), complicate interpretation of study outcome data, or otherwise interfere with achieving the study objectives.

6 STUDY PRODUCT

MTN-045 will not involve the administration of any study product.

7 STUDY PROCEDURES

7.1 Study Visits

Approximately 400 couples will be enrolled (see [Section 10.3](#) for sample composition details). Participants may be screened either separately or together with their partner, and site staff may explain the study to participants either separately or together with their partner, but other key components of participants' consent will be solicited separately to reduce the potential for participant coercion (see [Section 13.5](#) for additional details).

Survey questionnaires will be administered to each member of the couple separately. The individual questionnaires will be followed by a joint couple decision task completed by the couple together. Prior to completing the questionnaires, enrolled participants will receive an introduction to DPP products using standardized materials.

A subset of up to 80 participants (i.e., one or both partners from up to 40 couples) will be selected to complete a single post-survey explanatory IDI to provide further insight on the participants' survey responses and on any unexpected and/or interesting examples of experiences and behaviors relevant to the study endpoints.

Study visits may take place at the study clinic, at the participant's home, or at any other location agreed upon by the participant(s) and the study staff. Multiple visits may be conducted to complete all required procedures, if necessary.

7.1.1 Screening and Enrollment Visit Procedures

Table 1: Screening and Enrollment Visit Procedures

Screening and Enrollment Visit	
Component	Procedures
Administrative and Regulatory	
 • Confirm eligibility • Obtain written informed consent for screening and enrollment • Assign a unique Participant Identification (PTID) Number • Collect demographic data • Collect locator information • Provide reimbursement for study visit • Schedule next visit (if applicable)
Behavioral	
 • Provide introduction to DPP products via standardized materials • Administer behavioral questionnaire(s) individually • Administer behavioral questionnaire(s) as a couple

7.1.2 In-depth Interview Visit Procedures (for subset of participants only)

Table 2: In-depth Interview Visit Procedures

In-depth Interview Visit	
Component	Procedures
Administrative and Regulatory	
 • Update locator information • Provide reimbursement for study visit
Behavioral	
 • Conduct IDI

The IDI Visit may occur on the same day as the Screening and Enrollment Visit if agreed upon by the participant(s) and the study staff, but may be scheduled up to 28 days after the Screening and Enrollment Visit.

7.2 Behavioral Evaluations

The study will address questions related to the primary and secondary objectives of determining heterosexual couples' DPP product preferences and the underlying factors influencing those preferences, from the perspective of both partners in the couple. These questions will be assessed via behavioral questionnaires and IDIs conducted by trained interviewers. In addition, the study aims to gain further insight on:

- Motivations for DPP product use among couples with varying levels of risk for unintended pregnancy or HIV infection
- Motivations for DPP product use among couples with varying levels of male partner influence on the female partner's decision-making
- What effect, if any, knowledge of the product's efficacy would have on product preferences
- DPP product uptake, positioning, and other product roll-out issues

Additional questions and probes will be designed to delve further into the social and cultural norms that may play a role more broadly in DPP product preferences.

7.2.1 Survey Questionnaires

Participants will complete survey questionnaires, first separately from their partner, followed by a joint couple decision task where the couple will be asked to jointly indicate product attribute preferences and dislikes. The following will be assessed for all participants:

- Individual and relationship characteristics
- Interest in and willingness to use a DPP product
- Preferences among attributes of a DPP product

The survey questionnaires will measure preferences for a hypothetical DPP product by asking participants to select the products they would choose to prevent HIV and pregnancy from pairs of products with varying sets of attributes. Following each choice question, participants will be asked their preference between their chosen product and male condoms. They may also be asked to compare their preferred product, among those assessed, to longer-acting delivery forms such as injections or implants. Attributes may include:

- Product form (e.g. vaginal ring, oral tablets, vaginal insert, vaginal film)
- Duration or frequency of use
- Side effects
- Whether STI prevention could be included in product indication
- Whether it can be detected during sexual intercourse
- Hormonal vs. non-hormonal contraceptive

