Research engaging end-users as “co-designers” has demonstrated that understanding what product attributes are most influential to acceptability enables developers to make early product modifications and thus optimize a product’s chances for success.¹¹¹⁻¹¹³ The TRIO and QUATRO studies combined the use of placebo products and DCE methodologies to understand young African women’s preferences regarding a variety of MPT drug delivery forms in the context of HIV prevention.^{112,114-116} These studies used preference weights and relative importance scores to identify from a range of product attributes (i.e., dosage, mode of delivery, pregnancy prevention) which features end-users found most important across product formulations. Injections were favored by a majority of TRIO participants (chosen by 64% of participants after 3 months of using each of three products), but otherwise there were no clear favorites among the hypothetical MPT products evaluated in TRIO (oral tablets, VR, injections) or in QUATRO (VR, vaginal film, vaginal insert, vaginal gel). Product familiarity seemed to be a key component of participants’ preferences in both studies, given the increases in product ratings over time and with product use experience, as well as the preference for injections in TRIO, a widely prescribed method of contraception delivery in SSA. Lastly, although efficacy was rated as the most important product attribute in QUATRO, participants were willing to accept less efficacious methods if they exhibited other positive attributes (e.g., discreetness, ease of use, prevents pregnancy). Studies like TRIO and QUATRO underscore the importance of providing a menu of prevention choices to fit the variety of settings in which women live.

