3.3 Exploratory Objectives

- To explore relationship dynamics and their influences on the decision-making process for individuals and couples.
- To explore the extent to which male partner interest for, or acceptance of, a DPP product influences the female partner's willingness to use the product.
- To estimate uptake of a range of potential DPP products that can be incorporated in cost-effectiveness modelling of future products.

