10.3 Sample Size and Composition

The study will enroll approximately 400 heterosexual couples across the study sites. Women who are currently using contraceptives as well as those not using contraceptives will be eligible. Couples who are living together as well as those not living together will be eligible. Community-based recruitment will be conducted through stakeholder engagement with consultation from CAB members. Participants will complete survey questionnaires, first separately from their partner, then followed by a joint couples' decision task. Up to 80 participants, i.e., one or both partners from a subset of up to 40 couples, will be selected to complete an IDI.

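### The choice tasks offer male condoms but no neither or current-method answer, so uptake estimated from them for cost-effectiveness modelling may be biased upward

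*Protocol*

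**What the plan says.** Section 7.2.1 describes the task. Participants select a product "from pairs of products with varying sets of attributes". Then: "Following each choice question, participants will be asked their preference between their chosen product and male condoms". The next sentence adds a further, optional comparison: "They may also be asked to compare their preferred product, among those assessed, to longer-acting delivery forms such as injections or implants". The same section lists interest in and willingness to use a product as a separate item for all participants. The attribute list is introduced with "Attributes may include"; six items follow, and efficacy is not one of them.

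The use made of the data is in section 3.3: "To estimate uptake of a range of potential DPP products that can be incorporated in cost-effectiveness modelling of future products". The matching exploratory endpoint in the protocol summary takes the likelihood of using each product, overall and by subgroup, from analysis of the discrete choice experiment (DCE).

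On who answers, section 10.3 says: "Women who are currently using contraceptives as well as those not using contraceptives will be eligible". Section 5.3, criterion 4, requires each partner to express interest in contraception, HIV prevention or both. Section 13.7.1 does not exclude pregnant women.

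On efficacy, section 7.2 lists as something to learn: "What effect, if any, knowledge of the product's efficacy would have on product preferences". Section 2.5 reports that "efficacy was rated as the most important product attribute in QUATRO".

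**The concern.** A predicted probability of use depends on the set of alternatives offered. Here the fixed set is product A, product B and male condoms. A woman content with her present contraceptive, or a couple interested in only one of the two indications, may want none of these. As the task is described, such a respondent must still be recorded as taking the product or condoms.

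Condoms are a narrow benchmark on the protocol's own account. Section 2.1 notes that women may be unable to negotiate their use and that couples may be unwilling to use them. Sections 2.5 and 2.6 describe injectables as familiar and preferred, yet the comparison with injections is the optional one.

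At stake is the exploratory uptake estimate. An inflated value carried into a cost-effectiveness model would overstate coverage. An analysis plan can change how uptake is computed, but it cannot recover an answer that was never offered.

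**Working it through.** The protocol states no uptake value and no utilities, so there is no figure of its own to reproduce. The check has three parts.

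**1. Set the passages side by side.** Uptake comes from the DCE (exploratory endpoint). The DCE's fixed alternative is condoms (7.2.1). The eligible population includes people for whom a current method, or nothing new, is a realistic choice (10.3; 5.3, criterion 4). No described answer captures that choice.

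**2. Direction.** In a random-utility model, adding an alternative cannot raise the share of those already present. Leaving out a realistic one can therefore only raise the product's predicted share or leave it unchanged.

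**3. Size, as illustration only.** All utilities below are assumed. Use a fixed-coefficient logit with condom utility 0 and product utility V. If s is the share choosing the product over condoms alone, then exp(V) = s/(1−s). Add a neither/current-method option with utility Vo:

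share = exp(V) / (exp(V) + 1 + exp(Vo)) = s / (1 + (1−s)·exp(Vo))

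For s = 0.70 and Vo = 0: 0.70 / (1 + 0.30 × 1) = 0.70/1.30 = 0.538.

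| Share against condoms only | Vo = −3 | Vo = −2 | Vo = −1 | Vo = 0 | Vo = +1 |
|---|---|---|---|---|---|
| 50% | 48.8% | 46.8% | 42.2% | 33.3% | 21.2% |
| 70% | 69.0% | 67.3% | 63.0% | 53.8% | 38.6% |
| 90% | 89.6% | 88.8% | 86.8% | 81.8% | 70.8% |

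For the 70% row the overstatement is 70 − 69.0 = 1.0 point at Vo = −3, 70 − 53.8 = 16.2 points at Vo = 0, and 70 − 38.6 = 31.4 points at Vo = +1.

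This model makes the new option draw proportionally from product and condoms. If those who want neither would otherwise all have answered condoms, the product share does not move. The planned random parameters logit could fall anywhere between these patterns.

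**The case against.** The strongest reply is that the design already records refusal. Anyone who picks condoms in the follow-up has declined the product, so the task does not merely divide adopters among products. That is right, and it limits the bias: a reader might infer that the data give only shares among adopters, and the documents do not support that. It does not remove the bias, because a respondent who prefers the product to condoms but would in practice keep the current method still counts as uptake.

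The other comparisons help only in part. The injection or implant question is optional and is asked about the preferred product, not after every choice. The willingness item is asked of everyone, but the endpoint names the DCE as its source. The uptake calculation itself is not described, so certain bias cannot be claimed.

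A reader might also try to size the bias from the unmet-need figures in section 2.1 (33% for Uganda, 9.9% for Zimbabwe), treating them as the share q who would choose nothing and inflating by 1/(1−q). That is not supported. The section defines unmet need as wanting to avoid pregnancy without using a modern method, which describes plausible adopters rather than refusers. The figures are also national, whereas both partners in this sample must have expressed interest.

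A further tempting reading is that the product-form weights in the primary model are confounded with guessed efficacy. The documents do not show this. The attribute list is open, section 7.2 already plans to address knowledge of efficacy, and the standardized introduction in section 7.1 is not shown and may state a common efficacy. If efficacy is understood to be equal for all products, this distortion is zero.

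**Conclusion.** The concern holds for uptake. Section 7.2.1, followed as written, gives no way to choose neither product nor condoms, and the exploratory uptake endpoint rests on those data. The bias, if present, is upward. Its size cannot be calculated from the documents: it is negligible if the omitted option is unattractive and large if it rivals condoms (about 1 to 31 points from a 70% starting share, on the assumed utilities and proportional substitution above). It concerns an exploratory objective; the choices between products used for the primary attribute model are not affected by the missing answer.

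The conclusion assumes that the questionnaire follows section 7.2.1. If the instrument already has an opt-out, the protocol text only needs to be brought into line.

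Efficacy is a request for clarification. It is neither listed as an attribute nor said to be held constant, so form weights may absorb whatever efficacy respondents assume. Neither the sign nor the size of that can be given.

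**What to change.** Keep the A-versus-B choice first. Then make the follow-up three-way: the chosen product, male condoms, or neither/keep the current method. Use the third answer as the opt-out when predicting uptake, and say so where the uptake endpoint is defined. Report uptake as applying to couples in which both partners expressed interest (section 5.3, criterion 4), so that a cost-effectiveness model does not apply it to all couples.

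For the clarification, state in section 7.2.1 whether efficacy is varied or fixed. If it is fixed, give one common HIV and pregnancy efficacy for all products in the introduction and on the choice cards. A single closing question that changes it would serve the aim in section 7.2.

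The cost is questionnaire wording, settled before fielding. Respondents who take the third answer give slightly less information on the direct product-versus-condom contrast. The A-versus-B data for the primary model are unchanged.

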7.2.2 In-Depth Interviews (IDIs)

A subset of couples will be asked to complete an IDI. Site staff may ask one or both partners to complete an IDI, and IDIs may be conducted either individually or as a couple. IDIs will include, but not be limited to, topics such as:

- Communication and decision-making within the relationship, both for sexual and reproductive health decisions and for more general decisions
- Descriptions of HIV and pregnancy prevention practices
- Main challenge(s) and facilitator(s) encountered with use of contraceptive methods
- Main challenge(s) and facilitator(s) encountered with use of HIV prevention methods
- Other factors (e.g., situational, relationship, social/cultural/economic, sex and menstruation related, etc.) influencing potential DPP product use patterns (e.g., uptake, sustained use)
- Recommendations for “real world” implementation (e.g., overcoming financial barriers, marketing of DPP products)

IDI guides will be developed by qualified social scientists and administered by qualified interviewers. Guides will contain key research questions relating to the main topics of interest and suggested probes. Interviews and discussion sessions will be audio-recorded and transcribed into English (using a 1-step translation/transcription process).

Various tools may be used to facilitate interviews and discussion of sensitive topics with IDI participants. These may include, but not be limited to, visual displays of various drug delivery forms and show-cards listing topics and themes previously elicited in other studies.

8 ASSESSMENT OF SAFETY

MTN-045 is a minimum-risk research study. It does not involve a study product nor involve clinical, laboratory or other procedures associated with significant risk to participants. Therefore, few safety concerns are expected as a result of study participation; see [Section 13.4.1](#) for expected risks of study participation. The study site IoR is responsible for continuous monitoring of all study participants and for alerting the protocol team if unexpected safety events arise. Study sites will have written procedures for ensuring prompt reporting to the IRB/EC of any unanticipated problem involving risks to subjects or others. No safety events will be captured in the study database, except for social harms (see [Section 8.2](#)).

8.1 Safety Monitoring

Site IoRs are responsible for continuous close safety monitoring of all study participants, and for alerting the protocol team if unexpected concerns arise. Since the safety risks are minimal in this study, if any such unexpected concerns arise, site study staff must make the site IoR aware. The site IoR will provide follow-up guidance to the appropriate on-site staff member (e.g., site clinician, counselor, nurse, etc.). Study sites will take steps during pre-screening and screening activities to minimize the potential for partner coercion or for placing participants at increased risk of IPV; see [Section 13.5](#) for details. Additionally, an SOP for emergency procedures will be developed for the MTN-045 site staff to be used in situations of social harm and when situations that require immediate attention are identified, including IPV and suicidal ideation or behavior. The SOP will provide clear guidelines for site staff to refer participants in these situations to the relevant institution/body and to provide feedback to the protocol team.

The Manual for Expedited Reporting of Adverse Events to DAIDS will not be used for this study for the following reasons: 1) this study does not involve a study drug and is non-invasive; and, 2) adverse events are not primary or secondary objectives of the study. Untoward clinical or medical

occurrences reported by study participants to have been experienced during study participation will be recorded in participant file notes.

8.2 Social Harms

Although study sites will make every effort to protect participant privacy and confidentiality, it is possible that participants' involvement in the study could become known to others and that social harms – non-medical adverse consequences – may result. For example, participants could be treated unfairly, or could have problems being accepted by their families, partners and/or communities. Social harms that are judged by the IoR/designee to be related to study participation will be captured via case report form (CRF) and reported to the DAIDS Medical Officer (MO), Protocol Chairs, and responsible site IRBs/ECs according to their individual requirements beginning at the time of enrollment (i.e., after participants sign the informed consent and eligibility is confirmed) until study participation is complete. In the event that a participant reports social harm, every effort will be made by study staff to provide appropriate care and counseling to the participant, and/or referral to appropriate resources for the safety of the participant as needed. Each site will provide such care and counseling in accordance with standardized guidance provided in the MTN-045 Study Specific Procedures (SSP) Manual. While maintaining participant confidentiality, study sites may engage their CABs in exploring the social context surrounding instances of social harm.

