4.4 Expected Duration of Participation

Most participants will complete all study procedures in a single study visit, including administrative and data collection procedures. Participants who are selected for an IDI may require a second study visit if it is not feasible to complete the IDI at the initial visit. Additional visits may be conducted to complete all required procedures, if necessary.

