13.4 Risk Benefit Statement

13.4.1 Risks

It is not expected that this study will expose human subjects to unreasonable risk. Participation in this research includes the risks of loss of confidentiality and discomfort with the personal nature of questions when discussing sexual behaviors and DPP product preferences.

Psychological Harms

MTN-045 will ask questions that may cause individuals discomfort given their personal nature. Stress and feelings of guilt or embarrassment may arise simply from thinking or talking about one's own behavior or attitudes on sensitive topics, particularly during the couples' interview. This could result in undesired changes in thought and emotion or in tension within the couple.

While steps have been taken to minimize the risk of psychological harms (see [Section 13.5](#) for details) and while study staff will inform participants that they can choose not to answer questions at any time, study staff will collect information on participants who report a change in mood as a result of study participation. In addition, study staff will ensure that participants have access to proper clinical resources to address psychological harms.

Social Harms

Although study sites make every effort to protect participant privacy and confidentiality, it is possible that participants' involvement in the study could become known to others, and that social harms may result (i.e., because participants could become known as HIV-positive or at "high risk" for HIV infection). For example, participants could be treated unfairly or discriminated against, or could have problems being accepted by their families and/or communities.

Furthermore, it is possible that talking about one's own behavior or attitudes on sensitive topics during the couples' interview could lead to relationship problems for one or both partners. It is also possible that one partner could be coerced into study participation by the other, or that study

participation could put one partner at increased risk for IPV. Sites will take steps to minimize those possibilities (see [Section 13.5](#) for details).

Data on the occurrence of social harms will be collected from all participants. These data will be captured via CRF and analyzed on an ongoing basis. The protocol team will monitor, evaluate and adjust operations to reduce the potential for such occurrences.

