13.5 Informed Consent Process

Each study participant will provide written informed consent prior to completing any study procedures. In obtaining and documenting informed consent, the IoR and their designees will comply with applicable local and US regulatory requirements and will adhere to GCP and to the ethical principles that have their origin in the Declaration of Helsinki. Study staff must document the informed consent process in accordance with the Requirements for Source Documentation in DAIDS Funded and/or Sponsored Clinical Trials (<https://www.niaid.nih.gov/sites/default/files/daids-sourcedocpolicy.pdf>) and the relevant source documentation appendix (<https://www.niaid.nih.gov/sites/default/files/sourcedocappndx.pdf>). Participants will be provided with copies of the informed consent forms if they are willing to receive them.

In addition to informed consent forms, the protocol team will work with study staff and community representatives to develop appropriate materials about the study and a standardized approach to the informed consent process to be implemented at all study sites, which will be detailed in the MTN-045 SSP Manual. For example, potential participants may be asked to disclose their interest in HIV prevention and contraception during pre-screening activities to ascertain presumptive eligibility to enroll in MTN-045. Potential participants may also be privately asked whether they believe that participation in MTN-045 could place them at risk for experiencing IPV. Study staff will explain to all participants that some of the study activities, including some of the questionnaires, will be completed together with their partner. Only those potential participants who express interest in HIV prevention and/or contraception, and only those potential participants who do not express IPV-related concerns and/or do not raise concerns about participant safety among study staff, would be considered for further screening.

Study staff will explain the study to both members of the couple and determine their presumptive eligibility to participate in the study; both of these informed consent process components may be done with the potential participants either separately or together as a couple. However, to reduce the potential for coercion, study staff will assess each participant's willingness to be in the study and confirm their eligibility separately from their partner; participants will also sign individual

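### The window for recording social harms closes when participation ends, normally after a single visit, so most delayed harms from the couple session fall outside the only safety dataset

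*Protocol*

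**What the plan says.** **Capture window.** Section 8.2 of the protocol has social harms that the site judges related to participation recorded on a CRF and reported to the DAIDS Medical Officer, the Protocol Chairs and the IRBs/ECs, "beginning at the time of enrollment (i.e., after participants sign the informed consent and eligibility is confirmed) until study participation is complete".

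**Length of participation.** Section 4.4 states: "Most participants will complete all study procedures in a single study visit, including administrative and data collection procedures". It foresees two exceptions. One is the interview subset, some of whom may have to come back because the IDI could not be fitted into the enrollment day. The other is unfinished work: "Additional visits may be conducted to complete all required procedures, if necessary".

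**Named harms.** Section 8.2 gives as examples unfair treatment and difficulty being accepted by family, partners or community. Section 13.4.1 adds that "talking about one's own behavior or attitudes on sensitive topics during the couples' interview could lead to relationship problems for one or both partners", and that taking part could raise one partner's risk of IPV.

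**Purpose of the data.** Section 13.4.1 also says: "Data on the occurrence of social harms will be collected from all participants". These data are to be analyzed as the study runs so that the team can adjust operations. Section 8 makes social harms the only safety events held in the study database.

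**Screening.** Section 5.4 excludes a couple when participation would be unsafe, IPV risk included. Section 13.5 says: "Potential participants may also be privately asked whether they believe that participation in MTN-045 could place them at risk for experiencing IPV".

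**The concern.** A cross-sectional survey has almost no follow-up, so a rule that ends recording with participation ends it almost as soon as the exposure has occurred. The harms listed in sections 8.2 and 13.4.1 are mainly things that happen once the couple is back in its ordinary life: a quarrel later, a reaction from relatives, participation becoming known in the community. Under the written rule, such an event need not be entered on the CRF unless the participant still has a visit to come.

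At stake is the monitoring commitment, not any efficacy or preference estimate. If delayed harms are not recorded, the ongoing analysis promised in section 13.4.1 works mainly from what surfaces during the visit itself. A low count could not then be taken to describe what followed the couple session.

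The screening wording is a smaller, related matter. The IPV exclusion depends on the risk coming to light, yet the one question aimed directly at it is optional.

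**Working it through.** The protocol gives no social-harm rate or target, so there is no planned figure to reproduce. The check sets the sections side by side and counts who could have a longer window.

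**1. When the window opens and closes.** It opens at consent with confirmed eligibility and closes when participation is complete (section 8.2). Completion is not defined separately. Section 4.4, on expected duration, is the only guide and points to one visit for most participants.

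**2. Where the couple session falls.** Sections 7.1 and 7.2.1 place the joint task after the individual questionnaires. In Table 1 the couple questionnaire is the last behavioral item, and a next visit is scheduled only where applicable. Neither Table 1 nor Table 2 lists a later contact to ask about harm.

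**3. Who could have a longer window.**
- Participants: 400 couples × 2 = 800 (sections 5.1, 7.1 and 10.3).
- IDI subset: at most 80 participants, from up to 40 couples (sections 7.1 and 10.3). 80 / 800 = 10%.
- No IDI: at least 800 − 80 = 720. 720 / 800 = 90%.
- The IDI may be held on the enrollment day or up to 28 days later (section 7.1.2). So even for the 10%, the extension lies between zero and 28 days.
- An additional visit to finish procedures would lengthen the window for whoever needs one. The protocol gives no number for these, so the 720 describes who has no IDI, not exactly who has a single visit.

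**4. Window against named harms.**

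| Harm named as possible | Where | Likely to show before the visit ends? |
|---|---|---|
| Unfair treatment; non-acceptance by family, partner or community | 8.2, 13.4.1 | Mostly not |
| Relationship problems after the couples' interview | 13.4.1 | Partly: tension may show at once, consequences later |
| Increased IPV risk | 13.4.1 | Mostly not |

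The last column is a judgement about timing, not a figure from the protocol. Section 2.4 supports it: it cites physical violence, abandonment and divorce linked to partner involvement or disclosure in other programs.

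**5. Whether another dataset fills the gap.** Social harms are the only safety events in the database (section 8). Medical occurrences go to file notes and carry the same limit of having been experienced during participation (section 8.1). No Study Monitoring Committee will review the study (section 10.4).

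**6. Screening.** IPV risk is an exclusion (section 5.4), eligibility must be confirmed apart from the partner, and anyone who voices an IPV concern goes no further (section 13.5). The private question that would bring such a concern out is permitted but not required.

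**The case against.** The strongest reply is that this is a gap in record-keeping, not in protection. Site investigators monitor safety continuously, an emergency SOP covers social harm and IPV with feedback to the protocol team, unanticipated problems go promptly to the IRB/EC, and care and referral are offered (sections 8, 8.1, 8.2 and 9). None of these has a stated end date, and section 13.5 requires the consent process to cover what to do if harm occurs. This stands: a later spontaneous report could be acted on. It does not close the gap, because none of these provisions requires a CRF entry after participation ends.

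Four stronger readings are tempting, and the protocol does not support them.

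- **That relationship problems and IPV are the study's main risks.** The summary sentence in section 13.4.1 names loss of confidentiality and discomfort. The others are listed as possible, and IPV is tied to participation in general.
- **That a couple with a known IPV risk could be enrolled.** Section 5.4 excludes them and section 13.5 requires separate confirmation of eligibility. What remains is a risk that the participant knows of but is not asked about. The optional question also sits among examples of a process to be detailed in the SSP Manual, which may make it routine.
- **That the ongoing review would receive no signal.** Harms during a visit are recorded, and the open-ended channels above can carry later ones.
- **That the harm rate will be near zero by construction and read as proof of safety.** No such rate, and no safety endpoint, is planned. The count of 720 shows who lacks an IDI, not how many harms would be missed.

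It is also fair to say that participant-initiated reporting will still under-count, and that 28 days was set for scheduling interviews, not as a harm window. Both points are carried into the fix.

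**Conclusion.** The point holds in a limited form. Read together, sections 8.2 and 4.4 end CRF capture and reporting of social harms at the close of one visit for most participants, with at least about 720 of 800 (90%) having no IDI that could extend it. That does not fit the section 13.4.1 commitment to collect these data from all participants and to act on them, because most delayed harms that the protocol names would fall outside.

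The conclusion rests on two assumptions: that participation is complete when the last required procedure is done, which is the natural reading of section 4.4, and that the named harms mostly emerge after the visit. If the sponsor intends a later end point, section 8.2 needs to say so.

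It is a should-fix. The study gives no product and is described as minimum-risk, and no objective, endpoint, sample size or preference estimate depends on it. The optional IPV question is a secondary wording point.

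**What to change.** **Section 8.2.** Replace the end point with a fixed period after the joint couple task that applies to every participant. Twenty-eight days is one available anchor, since section 7.1.2 already uses that interval for the IDI visit; the length is the sponsor's choice. Record on the CRF any related social harm reported to the site in that period, and tell participants at the visit how to report one.

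**Reporting.** Present the count together with its window, and state that ascertainment after the visit is passive and will under-count.

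**Section 13.5.** Change the private IPV question from something sites may ask to something they will ask, of each partner separately, so that the exclusion in section 5.4 rests on a question that is always put.

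**Cost.** Short wording changes, one private question per participant where it is not already asked, and slightly more CRF work. Participant-initiated reports need no new visit. The recorded number of social harms may rise.
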